## APPENDIX B: LABORATORY EVALUATIONS

### Hematology:

Hematocrit (Hct; %)  
Hemoglobin (Hgb; g/dL)  
Mean corpuscular hemoglobin (MCH; pg)  
Mean corpuscular hemoglobin concentration (MCHC; g/dL)  
Mean corpuscular volume (MCV; fL)  
Platelet count (K/ $\mu$ L)  
Red blood cell (RBC) count (M/ $\mu$ L)  
White blood cell (WBC) count with differential (K/ $\mu$ L)

### Urinalysis:

Appearance  
Bilirubin  
Color  
Glucose  
Ketones  
Microscopic examination of sediment  
Nitrite  
Occult blood  
pH  
  
Protein  
  
Specific gravity  
Urobilinogen  
  
Serum beta human chorionic gonadotropin (hCG) (only for females who are not diagnosed as postmenopausal)  
Single antigen bead (SAB) assay, Human Leukocyte Antigen (HLA) and anti-HLA antibodies assays  
  
ELISpot assay

### Serum Chemistry:

Albumin (ALB; g/dL)  
Aspartate aminotransferase (AST [SGOT]; U/L)  
Alkaline phosphatase (ALK-P; U/L)  
Alanine aminotransferase (ALT [SGPT]; U/L)  
  
Blood urea nitrogen (BUN; mg/dL)  
  
Creatinine (mg/dL)  
Creatine kinase and subtypes (Ng/ml)  
Glucose (mg/dL)  
Lactate dehydrogenase (LDH; U/L)  
Potassium (K; mmol/L)  
Sodium (Na; mmol/L)  
Total bilirubin (mg/dL)  
Direct bilirubin (mg/dL)  
Total protein (G/dL)

Hemoglobin A1c (HbA1c; %) (screening only)

Troponin I (preferable) or Troponin T if Troponin I is not available (ng/ml)  
N-terminal pro-hormone brain natriuretic peptide (NT-proBNP; pg/ml)

Coagulation: (Infusion Visit only - for patients taking Coumadin)  
Activated partial thromboplastin time (PTT; sec)

International Normalized Ratio (INR)  
Hepatitis B surface Antigen (HBsAg), Hepatitis C Virus (HCV)  
Human Immunodeficiency Virus (HIV)

## APPENDIX C: TABLES OF CONTENTS FOR TABLES, FIGURES, AND LISTINGS

### Tables

#### STUDY POPULATION

- 14.1.1 Number of Subjects by Study Visit
- 14.1.2 Subject Disposition
- 14.1.3.1 Inclusion/Exclusion Criteria Not Met
- 14.1.3.2 Protocol Violations
- 14.1.4 Analysis Populations
- 14.1.5 Demographics and Baseline Characteristics
- 14.1.6.1 General Medical History
- 14.1.6.2.1 Cardiac Medical History, Index MI
- 14.1.6.2.2 Cardiac Medical History, Pre-Index MI
- 14.1.7.1 Screening Labs
- 14.1.7.2 Coagulation
- 14.1.8.1 Investigational Product Administration
- 14.1.8.2 Complications During Investigational Product Administration
- 14.1.8.3 Complications Within 24 Hours of Investigational Product Administration

#### EFFICACY

- 14.2.1 MRI Parameters
- 14.2.2 6MWT
- 14.2.3 NYHA
- 14.2.4.1 MLHFQ
- 14.2.4.2 SF-36
- 14.2.4.3 WPAI:SPH
- 14.2.5 Patient Global Assessment
- 14.2.6 NT-proBNP

#### SAFETY

- 14.3.1.1.1 Primary Safety Endpoint
- 14.3.1.1.2 Secondary Safety Endpoints
- 14.3.1.2 Summary of Treatment-Emergent AEs
- 14.3.1.3 Incidence and Number of Treatment-Emergent AEs
- 14.3.1.4 Peri-Procedural AEs
- 14.3.1.5 Treatment-Emergent Adverse Events in Subjects with Peri-Procedural Troponin Elevations
- 14.3.1.6 Treatment Emergent AEs Resulting in Study Discontinuation
- 14.3.1.7 Treatment Emergent SAEs
- 14.3.1.8 Peri-Procedural SAEs
- 14.3.1.9 Treatment-Emergent SAEs in Subjects with Peri-Procedural Troponin Elevations
- 14.3.1.10 Deaths
- 14.3.5.1.1 Serum Chemistry
- 14.3.5.1.2 Serum Chemistry Out of Range
- 14.3.5.1.3 Serum Chemistry Shifts From Baseline
- 14.3.5.2.1 Hematology
- 14.3.5.2.2 Hematology Out of Range
- 14.3.5.2.3 Hematology Shifts From Baseline
- 14.3.5.3.1.1 Urinalysis continuous
- 14.3.5.3.1.2 Urinalysis categorical
- 14.3.5.3.2 Urinalysis Out of Range
- 14.3.5.3.3 Urinalysis Shifts From Baseline
- 14.3.5.5.1 Serum Biomarkers
- 14.3.5.5.2 Serum Biomarkers Out of Range
- 14.3.5.5.3 Serum Biomarkers Shifts From Baseline
- 14.3.5.6.1 Cardiac Enzymes

- 14.3.5.6.2 Cardiac Enzymes Out of Range
- 14.3.5.6.3 Cardiac Enzymes Shifts From Baseline
- 14.3.5.7.1 NT-proBNP
- 14.3.5.7.2 NT-proBNP Out of Range
- 14.3.5.7.3 NT-proBNP Shifts From Baseline
- 14.3.5.9 ELISPot
- 14.3.6.1.1 Concomitant Medications
- 14.3.6.1.2 Concomitant Cardiac Medications of Interest
- 14.3.6.2 Vital Signs
- 14.3.6.3 Weight, Height, Body Mass Index
- 14.3.6.4 Cardiac Physical Examination
- 14.3.6.5.1 12-Lead Electrocardiogram
- 14.3.6.5.2 24-Hour Ambulatory Electrocardiogram/Holter
- 14.3.6.6 Echocardiography

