7.4.4 Expectedness

The following adverse events are considered to be expected as a result of the catheterization and infusion procedure:

- Disease-related adverse events are expected
- Some premature ventricular contractions, non-sustained ventricular tachycardia (<30 sec duration)
- Hypotension (Systolic Blood Pressure <80 mmHg) and/or bradycardia (Heart Rate <50 beats/min) that responds rapidly to fluid, atropine and possibly vasopressor administration, if required
- Reduction of coronary blood flow, TIMI flow grade I or II, persisting <3 min after balloon deflation, during cell infusion
- Angina, duration <10 min during cell infusion
- ST elevations, duration <3 min during cell infusion, troponin elevations above the 99th percentile but not more than 3x, at any time during the first 24 hours after cell infusion
- Coronary artery dissection
- Other risks of the infusion procedure include those risks that are possible with the study procedure. These include risks related to infection, bleeding, hypotension, pain and hematoma at the arterial puncture site, arrhythmia, sensitivity or allergy to radiographic contrast, exposure to radiation, thromboembolism, contrast induced nephropathy, myocardial ischemia or infarction.
- Bleeding, bruising and/or hematoma formation at the site of vascular access for the cell infusion procedure, at any time within the first 24 hours after cell infusion

All adverse events expected or otherwise, should be reported in the subject data. Serious Adverse

Events (SAEs) should be reported to the Sponsor within 24 hours of the site learning of the event.

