#### **7.2.1 Tables and Figures**

- Tables and figures will present data summaries and/or analyses for the appropriate study population; e.g., summaries of safety parameters will be shown for the safety population only.
- Treatment group order in tables and figures will be Recent CAP-1002, Recent Placebo, Chronic CAP-1002, Chronic Placebo, Overall CAP-1002, Overall Placebo.

- Tables and figures will present summaries/analyses by study visit window (see [Section 7.7](#)).
- Table column headers and figure legends will include subgroup sample sizes.

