### 10.3 AEs

AEs reported from screening through EOS will be coded according to MedDRA® (Medical Dictionary for Regulatory Activities) version 18.1. Each reported AE will be mapped to a Preferred Term (PT) and a System Organ Class (SOC). A subset of AEs (indicated below) will be adjudicated by the independent CEC.

A TEAE will be defined as an AE that began or worsened after the time of vascular access. AEs with insufficient date or time information to determine whether or not they were treatment-emergent will be considered treatment-emergent and the ambiguity regarding start time/date for these AEs will be footnoted in summary tables.

All reported TEAEs will be listed. Separate listings will be done for deaths, non-treatment-emergent AEs and serious AEs (SAEs), treatment-emergent SAEs, TEAEs within 24 hours of IP administration (adjudicated if related to IP or procedure), and TEAEs that resulted in study discontinuation (excluding deaths). Treatment-emergent SAEs will be adjudicated. The listing of deaths will include most appropriate category of death (e.g., CV, cerebrovascular, infection, malignancy, trauma/accident) and whether or not an autopsy was performed.

Incidence and number of TEAEs will be summarized by SOC and PTs within SOCs, both overall and by relationship to IP, relationship to IP administration, and severity. Relationship status “possibly,” “probably,” or “definitely” will be considered related and will be adjudicated. Missing relationship will be considered related and missing severity will be considered severe; the lack of assigned relationships for these AEs will be footnoted in summary tables. Only the most related TEAE per subject for a given PT will be counted in summaries by relationship; similarly, only the most severe TEAE will be counted in summaries by severity. Separate summaries will be done for TEAEs within 24 hours of IP administration (adjudicated if related to IP or procedure), treatment-emergent SAEs, treatment-emergent deaths, and TEAEs resulting in study discontinuation (excluding deaths). Each summary table will include a p-value for the comparison of incidence for each SOC and PT, as well as overall, between treatment groups. Product limit estimates of median time to death and 95% CIs will be calculated.

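### SAP Appendix C Tables 14.3.1.5 and 14.3.1.9 set adverse events by arm within a troponin-defined subset formed largely after infusion; between-arm p-values there would not be protected by randomisation (minor, supportive tables).

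*SAP*

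**What the plan says.** The SAFETY list in SAP Appendix C contains two tables restricted by troponin: Table 14.3.1.5, "Treatment-Emergent Adverse Events in Subjects with Peri-Procedural Troponin Elevations", and Table 14.3.1.9, "Treatment-Emergent SAEs in Subjects with Peri-Procedural Troponin Elevations". Listing 16.2.7.4 gives the corresponding by-subject adverse-event data.

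SAP 10.3 states: "Each summary table will include a p-value for the comparison of incidence for each SOC and PT, as well as overall, between treatment groups". It makes no exception for the troponin tables. It does not name them either: its list of extra summaries begins "Separate summaries will be done for TEAEs within 24 hours of IP administration (adjudicated if related to IP or procedure), treatment-emergent SAEs, treatment-emergent deaths" and ends with events leading to discontinuation. SAP 7.2.1 fixes the column layout: "Treatment group order in tables and figures will be Recent CAP-1002, Recent Placebo, Chronic CAP-1002, Chronic Placebo, Overall CAP-1002, Overall Placebo".

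Troponin and CK-MB are drawn about every 8 hours in the 24 hours after infusion (SAP 2.3.3), and once before it (Protocol 7.2.1 and Appendix 1). Protocol 7.7 lists their elevation among the events to be examined more closely.

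Neither document says what counts as a peri-procedural elevation. The candidates are:
- the expected-event list in Protocol 7.4.4, "troponin elevations above the 99th percentile but not more than 3x", which does not say what the 3x is a multiple of;
- more than 5 times the upper reference limit, from the peri-infusion MI definition (Protocol 9.5.1, SAP 2.3.1);
- the out-of-range flag of SAP 10.5.

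The time window is open too. The MI definition uses 24 hours, while the last biomarker window in SAP 7.7 runs to 28 hours. The troponin subset is not among the populations in SAP 6 or the subgroups in SAP 7.4.

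**The concern.** A table that compares arms only among subjects with a troponin rise conditions on something that happens after randomisation and largely after treatment. Protocol 1.3.3 attributes the procedural risk in both arms mainly to balloon inflation, so placebo subjects can enter the subset through the procedure. CAP-1002 subjects can enter through the procedure or, if the cells injure myocardium, through the cells as well. The two columns then hold different mixtures of patients, and a difference between them need not reflect any effect of treatment on adverse events.

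At stake is how a safety report is read. Side-by-side percentages with a p-value invite a treatment comparison, and this one may point the wrong way. With the threshold undefined, the subset could also be settled after the data are unblinded.

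**Working it through.** **Inputs.** The documents give no figure for these tables, so there is none to reproduce. Arm sizes are 69 CAP-1002 and 34 placebo (Protocol synopsis, Study Population); 103 split 2:1 gives 68.7 and 34.3, which agrees. The default test is two-sided at 0.05, with Fisher's exact test when any cell is below 5 (SAP 7.3). All troponin and adverse-event rates below are assumptions.

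**Model.** A share *a* of subjects has a rise from the procedure in either arm. A further share *c* has a rise only if given cells. The rest have none. Adverse-event risk is rA in the first group, rN in the last, and in the middle group rC0 without cells and rC1 with cells.

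- Difference in all infused subjects (CAP-1002 minus placebo) = c(rC1 − rC0).
- Difference in the troponin subset = (a·rA + c·rC1)/(a + c) − rA = c(rC1 − rA)/(a + c).

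The first is the real effect. The second depends on rA, which has nothing to do with the effect of the cells.

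**Three cases**, with a = c = 0.15 and rC0 = rN = 0.20:

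| rA | rC1 | All infused: CAP-1002 vs placebo | Subset: CAP-1002 vs placebo | Reading |
|---|---|---|---|---|
| 0.50 | 0.30 | 26.0% vs 24.5% (+1.5) | 40% vs 50% (−10) | reversed |
| 0.50 | 0.50 | 29.0% vs 24.5% (+4.5) | 50% vs 50% (0) | hidden |
| 0.30 | 0.50 | 26.0% vs 21.5% (+4.5) | 40% vs 30% (+10) | exaggerated |

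**Range.** Let a and c each run from 0.10 to 0.25.
- rA 0.40 to 0.50, rC1 0.30: the true difference is +1.0 to +2.5 points and the subset shows −2.9 to −14.3.
- rA 0.30, rC1 0.50: the true difference is +3.0 to +7.5 points and the subset shows +5.7 to +14.3.

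**Subset size.** Expected placebo members are 34 × 0.10 = 3.4 up to 34 × 0.25 = 8.5. In the three cases above they are 34 × 0.15 = 5.1, against 69 × 0.30 = 20.7 on CAP-1002. With 17 placebo subjects per stratum (34/2) and a = 0.10, a stratum column expects 1.7. In the reversed case, 63% of 200,000 simulated trials gave a subset estimate favouring CAP-1002.

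**Would a false protective p-value appear?** Usually not. With 17 vs 3 subjects and 7 vs 2 events, Fisher p = 0.57; with 21 vs 5 and 8 vs 2 events, p = 1.0.

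**A more extreme case**, with a = 0.10, c = 0.30, rA = 0.50, rC1 = 0.20 and rC0 = rN = 0.10:
- Subset: (0.05 + 0.06)/0.40 = 27.5% on CAP-1002 against 50% on placebo.
- All infused: 0.05 + 0.06 + 0.60 × 0.10 = 17% against 0.05 + 0.90 × 0.10 = 14%.
- Subset sizes: 69 × 0.40 = 27.6 and 34 × 0.10 = 3.4.
- Subset test: 8/28 vs 2/3 gives p = 0.24; 8/28 vs 3/3 gives p = 0.04.
- Troponin elevation itself: 28/69 vs 3/34 gives p = 0.001.
- In 20,000 simulated trials the troponin excess was significant in about 91%, and the subset gave a significant protective result in about 9%.

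**The case against.** The strongest reply is that nothing important depends on these tables. No endpoint, hypothesis or stopping guideline uses them. The SAP takes all infused subjects as its safety population (SAP 10) and plans the unconditioned comparison in Tables 14.3.1.3 and 14.3.1.7. Troponin is already reported as an outcome: SAP 10.5 plans out-of-range incidence and shift tables with arm p-values, and Appendix C lists Tables 14.3.5.6.1 to 14.3.5.6.3 for cardiac enzymes. Elevations above 5 times the limit with clinical evidence of infarction fall within the primary safety endpoint. All of this stands and sets the size of the point.

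Three further limits also stand. The p-value is inferred from a general sentence in SAP 10.3 that does not mention these tables, and Appendix C is only a table of contents. Describing what happened to subjects with elevations fits Protocol 7.7. A pre-infusion sample exists, so the infusion may not account for every elevation.

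A reader might infer that the plan would make harmful cells look protective, or would conceal an injury signal. The documents do not support that. Reversal needs cell-related rises to carry lower event risk than procedural ones, and no passage gives those risks. SAP 7.2.1 puts subgroup sample sizes in the column headers, so an imbalance such as 28 against 3 would be visible in the table itself.

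What the reply does not remove is the comparison. Read literally, the plan still produces p-values across arms in an undefined subset formed largely after treatment.

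**Conclusion.** The point holds as a minor one. Tables 14.3.1.5 and 14.3.1.9, carried out as SAP 10.3 reads, would compare arms within a subset that CAP-1002 may itself have shaped. Under the assumed rates the displayed difference can depart from the true one in either direction: −2.9 to −14.3 points shown against a true +1.0 to +2.5, or +5.7 to +14.3 shown against a true +3.0 to +7.5. It would rest on roughly 3 to 9 placebo subjects. Those ranges illustrate the mechanism and do not forecast the trial's result.

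The consequence is limited to how two supportive tables are read. The primary safety conclusion, sample size, power and alpha are unaffected.

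**What to change.** Before unblinding:

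1. State in SAP 10.3 that Tables 14.3.1.5 and 14.3.1.9 carry no between-arm p-values, and label both descriptive. Alternatively, replace them with the proportion of all infused subjects in each arm who had both an elevation and a TEAE (or SAE).
2. Define peri-procedural troponin elevation: the threshold with its reference, the time window, and the role of the pre-infusion sample. If the 3x of Protocol 7.4.4 is to be used, the sponsor must first say what it is a multiple of.
3. Add to the planned cardiac-enzyme tables the incidence of elevation by arm in all infused subjects at that threshold, and at more than 5 times the upper reference limit, which the peri-infusion MI definition already uses.

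Listing 16.2.7.4 can stay as it is. The cost is SAP wording, two table shells and an addition to the enzyme tables, with no new data. The downside is that the subset percentages no longer serve as an arm comparison.

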## Figures

### EFFICACY

- 14.2.1 MRI Parameters
- 14.2.2 6MWT
- 14.2.3 NYHA
- 14.2.4.1 MLHFQ
- 14.2.4.2 SF-36
- 14.2.4.3 WPAI:SPH
- 14.2.5 PGA
- 14.2.6 NT-proBNP

### SAFETY

- 14.3.5.1.X Serum Chemistry Box Plots, Laboratory Evaluation X
- 14.3.5.2.X Hematology Box Plots, Evaluation X
- 14.3.5.6.X Cardiac Enzymes Box Plots, Evaluation X

## Listings

STUDY POPULATION	
16.2.1.1	Critical Dates and Scheduled Visits
16.2.1.2	Subject Study Visits
16.2.1.3	Subject Disposition
16.2.2.1	Informed Consent and Eligibility
16.2.2.2	Protocol Violations
16.2.2.3	Missed Visits and Assessments
16.2.3	Analysis Populations
16.2.4.1	Demographics
16.2.4.2.1	General Medical History
16.2.4.2.2.1	Cardiac Medical History, Index MI
16.2.4.2.2.2	Cardiac Medical History, Pre-Index MI
16.2.4.3.1	Pre-Treatment AEs
16.2.4.3.2	Pre-Treatment SAEs
16.2.4.4.1	Pre-Treatment General Medications
16.2.4.4.2	Pre-Treatment Cardiac Medications of Interest
16.2.4.5	Screening CT
16.2.4.6	Serology
16.2.4.7	Coagulation
16.2.5.1.1	Investigational Product Administration Part 1
16.2.5.1.2	Investigational Product Administration Part 2
16.2.5.2.1	Complications During Investigational Product Administration
16.2.5.2.2	Complications Within 24 Hours of Investigational Product Administration
EFFICACY	
16.2.6.1	MRI Parameters
16.2.6.2	6MWT
16.2.6.3	NYHA
16.2.6.4.1	MLHFQ
16.2.6.4.2	SF-36 Health Survey
16.2.6.4.3	WPAI:SPH
16.2.6.5	Patient Global Assessment
16.2.6.6	NT-proBNP
SAFETY	
16.2.7.1.1	Primary Safety Endpoint
16.2.7.1.2	Secondary Safety Clinical Endpoints
16.2.7.2.1	Treatment Emergent AEs
16.2.7.2.2	Treatment Emergent AEs as Reported
14.3.2.1	Treatment Emergent SAEs
16.2.7.3	Peri-Procedural AEs
14.3.2.2	Treatment Emergent AEs Resulting in Study Discontinuation
16.2.7.4	Treatment-Emergent AEs in Subjects with Peri-Procedural Troponin Elevations
14.3.2.3	Treatment-Emergent AEs Resulting in Death
16.2.7.5	Cause of Death
16.2.8.1	Serum Chemistry
14.3.4.1.1	Serum Chemistry Out of Range
16.2.8.2	Hematology
14.3.4.2.1	Hematology Out of Range
16.2.8.3	Urinalysis
14.3.4.3.1	Urinalysis Out of Range
16.2.8.4	Cardiac Enzymes
14.3.4.4.1	Cardiac Enzymes Out of Range
14.3.4.4.2	Cardiac Enzymes Clinically Significant
16.2.8.5	NT-proBNP
14.3.4.5.1	NT-proBNP Out of Range

- 16.2.8.6.1 HLA Profile
- 16.2.8.6.2 DSA Monitoring
- 16.2.8.7 ELISpot
- 16.2.8.8 Serum Biomarkers
- 16.2.9.1.2 Concomitant Medications
- 16.2.9.2 Concomitant Cardiac Medications of Interest
- 16.2.9.3 Vital Signs
- 16.2.9.4 Weight, Height, Body Mass Index
- 16.2.9.5.1 Cardiac Physical Examination
- 16.2.9.5.2 12-Lead Electrocardiogram
- 16.2.10 24-Hour Ambulatory Electrocardiogram/Holter
